1.3 Motivation for this study

Hospital readmission was more common in patients with mild hypertension prior to their primary delivery discharge. In addition, Hirshberg, et al discovered postpartum patients were less likely to be readmitted due to hypertension related complications if they were discharged on antihypertensive medication therapy. Treatment or surveillance strategies have been understudied for postpartum patients with hypertension. Demonstration of a decrease in hospital readmission with a novel mobile application may provide an effective method of preventing severe maternal postpartum hypertension related hospital readmission and associated maternal morbidities.

2. Objectives

Aim 1: Conduct an initial phase study for postpartum women at risk for severe hypertension to estimate the rates of willingness to participate in and utilize remote mobile health applications to monitor home blood pressures and weights, medication adherence after hospital discharge, to inform a trial to decrease postpartum maternal morbidity and readmission.

Sub Aim 1: Conduct a survey regarding patient satisfaction using mobile health technology

Hypothesis: We hypothesize that the mobile health application will be implemented with strong fidelity, have positive patient acceptability, and demonstrate a meaningful reduction in home blood pressures and postpartum hospital readmission.

Aim 2: Obtain prospective daily monitoring of blood pressures in the Peripartum period (initial hospital admission through 6 weeks postpartum) to understand natural history of development and resolution of postpartum hypertension using all patients utilizing the mobile health program over year 1. Specifically, this data will be used to estimate standard deviations of SBP and DBP in the intrapartum compared to 24-96 hours postpartum to inform a future trial regarding the threshold blood pressure to prevent development of severe hypertension or hospital readmission.

Hypothesis: We hypothesize women with severe intrapartum hypertension will predict development of severe hypertension within 7 days of delivery more often than blood pressures obtained in the first 24-96 hours after delivery.

Aim 3: Compare the maternal outcomes in the cohort utilizing remote patient monitoring to the cohort of patients with hypertension related disorders discharged with routine care. This would include all patients from Aim 1 as well as the remaining from the entire 1-year experimental period.

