Sub-Aim 5D: Compare the 6 week postpartum depression rates of the cohort utilizing remote patient monitoring to the cohort of patients with hypertension related disorders discharged with routine care.

Hypothesis: We hypothesize that women utilizing remote patient monitoring will have lower rates of depression than women with hypertension related disorders discharged with routine care.

Sub-Aim 5E: Correlate the results of the HoneyWell Biometrics Questionnaire question number 42 to the result of the Edinburgh Depression Scale recorded at the 6 week postpartum visit. (Question number 42 is: Has your mood been more depressed this week compared to a normal week? (Rated from 1-7))

Hypothesis: We hypothesize that the HoneyWell Biometrics Questionnaire question number 42 will capture more postpartum depression than the 6 week Edinburgh Depression Scale, but that it will correlate well.

Sub-Aim 5F: Graph the blood pressure trajectory of the cohort utilizing remote patient monitoring with daily weights over 6 weeks.

Hypothesis: This is a descriptive sub-aim. We hypothesize that the postpartum blood pressure will peak at 5-7 days postpartum.

Sub-Aim 5G: Compare the 6 week postpartum blood pressure of the cohort utilizing remote patient monitoring to the cohort of patients with hypertension related disorders discharged with routine care who attended their 6 week postpartum visit.

Hypothesis: We hypothesize that women utilizing remote patient monitoring will have lower blood pressures at their 6 week postpartum visit than women with hypertension related disorders discharged with routine care.

Specific Aim 6: Conduct a follow-up satisfaction from a medical provider perspective in having their patients cared through this study, as well as the betterment of the telehealth monitoring system for future clinical use. This will be collected anonymously from providers.

Hypothesis: We hypothesize that providers of patients enrolled in this study will have had a positive experience while caring for their subject.

Specific Aim 7: Descriptive analysis of exactly what happens to women who end up with developing a hypertensive disorder in pregnancy and blood pressure trend from baseline pregnancy through 6 weeks postpartum.

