The original study closed to accrual, with a total of 214 subjects enrolled, on June 11, 2018. With the success of the study, UPH-Meriter decided to incorporate the home monitoring program into its standard clinical services as of January 1, 2019. Through UPH-Meriter, 358 patients received services through this clinical program.

We would like to retrospectively review the patient data in Peridata for these 358 patients. We will collect home vital sign data to assess blood pressure trends from early pregnancy through pregnancy and postpartum. This additional data would help to increase our sample size in this evaluation. The same data would be collected from the clinical patients.

Hypotheses:

- 1) Baseline BP is lower than the 6 week postpartum after having a hypertension problem in pregnancy.
- 2) Postpartum blood pressure is highest in labor and then normalizes through 3 days postpartum with an abrupt increase 3-7 days postpartum.
- 3) Woman who normalize their blood pressure will do so by 14 days postpartum.

Specific Aim 8: Descriptive comparison of TeleHealth screening for depression, based on change of screening test from single question to Patient Health Questionnaire-9 (PHQ-9) in April 2019.

Hypothesis: We hypothesize that the change of screening test for depression from a single question to the PHQ-9 will be a more objective predictor of depression in TeleHealth patients.

ENDPOINTS:

Aim 1 primary endpoint: The primary endpoint is enrollment of 55 patients using the mobile health program each for a total 42 days postpartum.

Aim 2-5 primary endpoint: The primary endpoint is enrollment of up to 40 patients at all times (for a total of 42 days) over one year (220 experimental and 220 matched controls for chart review) **of the funded period for this project utilizing the proposed mobile health program as an option for postpartum hypertension surveillance.**

3. Selection criteria

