7.2 Analysis plan

Aim 1: Analysis of the primary outcome will be performed assessing rates of willingness to participate and patient retention in the study for 42 days postpartum. Secondary outcome measures will be attrition rate and compliance rates to both care and medication.

Aim 2: We will be developing an ROC curve with Youden’s index to predict the optimum SBP and DBP from intrapartum and postpartum to target for postpartum blood pressure thresholds for blood pressure management to prevent postpartum readmission due to severe hypertension.

Aim2-8: Baseline demographic and descriptive statistics will be compared to assess comparability of the study groups. Continuous variables will be assessed with student t-test and categorical data will be analyzed using ANOVA.

Aim 4: Analyses were performed to determine whether it is cost-effective to use Bluetooth-enabled tablets for postpartum blood pressure monitoring in comparison to standard monitoring in women with hypertension-related disorders of pregnancy. The data for the analyses will be derived from a prospective study at UnityPoint Health- Meriter Hospital where patients with hypertensive-related disorders of pregnancy will be enrolled in either standard management of blood pressure (routine nurse blood pressure visit 3-5 days from discharge) or monitoring with a Honeywell Genesis Android Touch Bluetooth remote patient monitoring system. Primary outcomes examined will include cost and readmissions.

8. Feasibility

Table #. UnityPoint Health-Meriter Data 2015. Total deliveries: 3873

Hypertensive disorder	Maternal (n=476)	Neonatal (n=147)
Chronic	87 (18%)	30 (20%)
Gestational, preeclampsia and SIPE	387 (81%)	115 (78%)
Eclampsia	2 (0.4%)	2 (1.4%)

** We anticipate that we will have approximately 40 patients with a hypertension related disorder for potential enrollment each month. At the beginning of the study, we only had 30 mobile health units that could have been used at any time. Effective 10/01/2017, an additional 10 mobile health units were acquired, making 40 mobile health units to available for study use at any time. We would strive to include all in the future as routine care if possible. We believe this project will be very successful in improving the quality of care for postpartum women at risk of developing severe complications associated with hypertension.

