APPENDIX I

Data variables to extract from EPIC Electronic Medical Records/Peridata

1. Medical record number for mother
2. Date of birth
3. Link baby to mother (Medical record number)
4. Date of birth

Demographics Maternal

5. Maternal age
6. Tobacco use
 - a. Yes
 - b. No
7. Date of first prenatal care visit
8. Body mass index at first prenatal care visit
9. Body mass index at delivery or with initial admission
10. Body mass index at second admission
11. Body mass index >30 at delivery
 - a. Yes
 - b. No
12. Maternal weight in kilograms with first prenatal care visit
13. Maternal weight in kilograms on initial admission
14. Maternal weight in kilograms within 24 hours of delivery
15. Maternal weight in kilograms within 24-48 hours of delivery
16. Maternal weight in kilograms within 48-72 hours of delivery
17. Maternal weight in kilograms within 72-96 hours of delivery
18. Maternal weight in kilograms within 24 hours of initial admission discharge
19. Maternal weight in kilograms on readmission
20. Maternal weight in kilograms on discharge from readmission
21. Maternal diabetes
 - a. Gestational
 - b. Type 1
 - c. Type 2
22. Marital status
 - a. Married
 - b. Single
 - c. Unknown
23. Insurance
 - a. Commercial
 - b. Medicaid
 - c. HMO
 - d. Uninsured
 - e. Other
 - f. Unknown
24. Race

- a. Caucasian
- b. Hispanic
- c. African American
- d. American Indian/Alaskan Native
- e. African
- f. Asian American
- g. Other
- h. Unknown

25. Ethnicity

- a. Hispanic

26. Gravidity

27. Parity (live children)

28. Gestational age rounded in weeks at delivery

29. Estimated date of delivery

30. Singleton pregnancy

- a. Yes
- b. No

31. Multiple pregnancy

- a. Twins
- b. Triplets

32. Mode of delivery

- a. Normal spontaneous vaginal delivery
- b. Operative delivery
 - i. Forceps
 - ii. Vacuum
- c. Cesarean section

33. Indication for cesarean section

- a. First stage arrest
- b. Second stage arrest
- c. Fetal intolerance of labor
- d. Fetal distress
- e. Repeat cesarean section
- f. Failed trial of labor after prior cesarean section
- g. Elective primary cesarean section
- h. Vaginal bleeding/abruption
- i. Placentation
- j. Fetal malpresentation
- k. Maternal illness
- l. Other

34. Hypertension related disorder was diagnosed in pregnancy

- a. Prior to initial admission
- b. Prior to delivery of baby (intrapartum)
- c. After delivery of baby (postpartum)
- d. Only upon readmission to hospital after initial admission discharge

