35. Specific hypertension related disorder diagnosed in pregnancy
 - a. Chronic
 - b. Gestational
 - c. Preeclampsia
 - i. Mild
 - ii. Severe features
 - d. Eclampsia

Demographics Neonatal

36. Birth weight in grams
37. Apgar score <7 at 5 minutes after birth
38. Oxygen required after 24 hours of delivery
 - a. CPAP
 - b. Nasal cannula
 - c. Intubation
39. Disposition
 - a. Mother baby unit
 - b. Progressive care nursery
 - c. Neonatal intensive care unit

Outcomes Maternal

40. Date and time of primary of admission for delivery
41. Date and time of secondary of admission for delivery
42. Date and time of emergency room visit for hypertension
43. Date and time of triage room visit for hypertension
44. Date and time of primary of discharge after delivery
45. Date and time of secondary of discharge after delivery
46. Number of initial admission days for length of stay
47. Number of secondary admission days for length of stay
48. Systolic blood pressure on admission with date and time
49. Diastolic blood pressure on admission with date and time
50. Date of postpartum visit
 - a. Date
51. Maternal weight in kilograms at 6 week postpartum visit (via Meriter Epic or UW Epic/ HealthLink)
 - a. Continuous variable
52. Breastfeeding status at the time of postpartum hospital discharge (via Meriter Epic)
 - a. Exclusive breastfeeding
 - b. Both breast and bottle feeding
 - c. Exclusively bottle feeding
53. Breastfeeding status at 6 week postpartum visit (via Meriter Epic or UW Epic/ HealthLink)
 - a. Exclusive breastfeeding
 - b. Both breast and bottle feeding
 - c. Exclusively bottle feeding

54. Maternal Edinburgh Depression Screen Score at 6 week postpartum visit (via Meriter Epic or UW Epic/ HealthLink)

- Score 0-30
- Positive or Negative
 - Positive (≥ 10)
 - Negative
- Suicidal

55. Contraception method utilized/ implemented at 6 week postpartum visit(via Meriter Epic or UW Epic/ HealthLink)

- None
- Natural family planning
- Condoms
- Combined oral contraceptive pills
- Progestin-only oral contraceptive pills
- Vaginal ring
- Depot medroxyprogesterone acetate
- Long acting reversible contraceptive
 - Copper IUD
 - Levonorgestrel IUD
 - Nexplanon

56. Blood pressure at 6 week postpartum visit (via Meriter Epic or UW Epic/ HealthLink)

- SBP
- DBP

57. Whether a referral to the primary care provider is discussed in the 6 week postpartum note (via Meriter Epic or UW Epic/ HealthLink)

- Yes
- No

Please report the top three values for the maximum values below

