
58. Maximum Systolic blood pressure during labor (top three) with date and time
59. Maximum Diastolic blood pressure during labor (top three) with date and time
60. Maximum Systolic blood pressure within 24 hours of delivery with date and time
61. Maximum Diastolic blood pressure within 24 hours of delivery with date and time
62. Maximum Systolic blood pressure on admission on 24-48 hours of delivery with date and time
63. Maximum Diastolic blood pressure on 24-48 hours of delivery with date and time
64. Maximum Systolic blood pressure on admission on 48-72 hours of delivery with date and time
65. Maximum Diastolic blood pressure on 48-72 hours of delivery with date and time
66. Maximum Systolic blood pressure on admission on 72-96 hours of delivery with date and time
67. Maximum Diastolic blood pressure on 72-96 hours of delivery with date and time
68. Maximum Systolic blood pressure within 24 hours of discharge date and time
69. Maximum Diastolic blood pressure within 24 hours of discharge date and time
70. Minimum Systolic blood pressure during labor (top three) with date and time
71. Minimum Diastolic blood pressure during labor (top three) with date and time
72. Minimum Systolic blood pressure within 24 hours of delivery with date and time
73. Minimum Diastolic blood pressure within 24 hours of delivery with date and time
74. Minimum Systolic blood pressure on admission on 24-48 hours of delivery with date and time

75. Minimum Diastolic blood pressure on 24-48 hours of delivery with date and time

76. Minimum Systolic blood pressure on admission on 48-72 hours of delivery with date and time

77. Minimum Diastolic blood pressure on 48-72 hours of delivery with date and time

78. Minimum Systolic blood pressure on admission on 72-96 hours of delivery with date and time

79. Minimum Diastolic blood pressure on 72-96 hours of delivery with date and time

80. Minimum Systolic blood pressure within 24 hours of discharge date and time

81. Minimum Diastolic blood pressure within 24 hours of discharge date and time

82. Blood pressure medications used prior to delivery of baby (used prior to initial admission due to chronic or gestational hypertension) with date and time of initiation if available.

- a. Atenolol
- b. Hydralazine
- c. Lasix
- d. Clonidine
- e. Labetalol
- f. Nifedipine
- g. Metoprolol
- h. Enalapril
- i. Other medication
- j. No medications

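### Appendix I assigns no blood pressure field to readmissions, emergency visits or triage visits, so severe readings taken there between 96 h and day 7 may be missed

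*Combined protocol and SAP*

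**What the plan says.** Three parts of section 2 look at BP in the first week after delivery:

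- Sub-Aim 5F, for the monitored cohort: "We hypothesize that the postpartum blood pressure will peak at 5-7 days postpartum".
- Aim 7, hypothesis 2: "Postpartum blood pressure is highest in labor and then normalizes through 3 days postpartum with an abrupt increase 3-7 days postpartum".
- Aim 2, where the predictor is severe hypertension during labour: it "will predict development of severe hypertension within 7 days of delivery more often than blood pressures obtained in the first 24-96 hours after delivery".

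Aims 3 and 5 also compare the incidence of reported severe hypertension between monitored women and routine-care controls. Section 7.2 gives the Aim 2 ROC analysis a different target: "postpartum blood pressure thresholds for blood pressure management to prevent postpartum readmission due to severe hypertension".

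After discharge, monitored women take three home readings a day, no more than five minutes apart. The average is used as the daily value (section 6). Chart data come from Appendix I:

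- **Readmission:** dates and length of stay (items 41, 45, 47), BMI and weight (10, 19, 20; for example "Maternal weight in kilograms on readmission"), drugs, intravenous route and magnesium (86, 88, 91, 94), and laboratory values (106).
- **Emergency and triage visits:** items 42-43 only, for example "Date and time of emergency room visit for hypertension".
- **Inpatient BP:** labour, then maxima and minima in windows timed from delivery. The last such maximum is "Maximum Systolic blood pressure on admission on 72-96 hours of delivery with date and time" and its diastolic counterpart (66-67).
- **Other BP:** on admission (48-49), within 24 hours of discharge (68-69, 80-81), and at the 6-week visit (56).

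**The concern.** In a study of postpartum hypertension, an unplanned hospital contact is where a very high pressure is likely to be measured. Section 1.1 says that women with symptoms are seen in emergency or triage departments. Section 6 links readmission to SBP of at least 160 or DBP of at least 110 with end-organ effects, at the provider's discretion. For these contacts Appendix I collects almost everything about a readmission except BP, and nothing but the time of an emergency or triage visit.

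Two things are at stake. First, a woman in hospital is not sending home readings, and the plan does not say how those days enter the 5F and Aim 7 curves. The missing days plausibly depend on BP. Second, a woman whose only severe reading was taken at such an encounter may be classed as free of severe hypertension. That affects the Aim 2 hypothesis outcome and the Aim 3 and 5 comparison. Controls have no home device, so for them these encounters are a main source of severe readings after discharge. Readings that are never extracted cannot be recovered in analysis.

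**Working it through.** The plan states no figure for this point, so there is none to reproduce. The check sets the BP fields against the windows in which the aims look.

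**1. Window coverage.** Take day d as 24 × d hours after delivery. The delivery-timed maxima (items 60-67) cover 0-96 h.

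| Window | Hours | Covered | Share |
|---|---|---|---|
| Aim 2 hypothesis, within 7 days | 0-168 | 96 of 168 | 57% |
| Aim 7 rise, days 3-7 | 72-168 | 24 of 96 | 25% |
| 5F peak, days 5-7 | 120-168 | 0 of 48 | 0% |

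If delivery counts as day 1, day 5 begins at 96 h and the 5F window is still uncovered.

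**2. Could another field hold the reading after 96 h?**

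- Items 48-49 do not say which admission. They follow items on both primary and secondary admissions, so a readmission value is possible but not assured.
- Items 68-69 do not say which discharge. Item 18, on weight, does specify the initial one.
- Even on the widest reading, none of these four items covers an emergency or triage visit that does not lead to admission.
- Home data keep a severe daily average recorded before or after the encounter. They do not hold the reading taken at it. Section 13.4 foresees submission by noon, so a rise later that day need not appear.
- For the 358 clinical-programme women, section 6 says that no data fields will be added, so the gap carries into Aim 7.

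**3. Effect on a daily mean, by assumption.** Let a share r of women be in hospital on a given day, with mean BP d mmHg above the mean m of the others. The full mean is (1 − r)m + r(m + d) = m + rd. The observed mean is m, so the understatement is r × d. The documents give neither r nor d.

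| r | Women of 214 | d = 15 | d = 30 |
|---|---|---|---|
| 1% | 2.1 | 0.15 mmHg | 0.3 mmHg |
| 2% | 4.3 | 0.3 mmHg | 0.6 mmHg |
| 5% | 10.7 | 0.75 mmHg | 1.5 mmHg |
| 10% | 21.4 | 1.5 mmHg | 3.0 mmHg |

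**4. Effect on case counts.** The number lost is N × (share with such an encounter by day 7) × f. Here f is the share of those women who were severe at the encounter and have no severe reading in any other recorded source. The documents give neither share, and f can lie anywhere from 0 to 1, so no case-loss figure can be derived.

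**The case against.** The strongest case on the other side has four parts.

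**The highest readings are not shown to be lost.** A reader might infer that they drop out of the dataset. The documents do not support that. Home values are reviewed daily, and a high one that prompts a visit stays in the home data. The 72-96 h windows are timed from delivery and can include an early readmission. Items 48-49 and 68-69 are ambiguous, which does not prove that the data are absent. This stands, and it limits the point to readings that may be missed after 96 h.

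**The planned Aim 2 analysis is not undone.** A reader might infer that the ROC outcome fails. Section 7.2 directs it at readmission, which is dated (items 41, 101). Emergency and triage visits for hypertension are dated too. This stands. The exposed outcome is the one in the Aim 2 hypothesis: "severe intrapartum hypertension will predict development of severe hypertension within 7 days of delivery".

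**Loss because of high BP is an inference.** Readmission is at the provider's discretion and also involves end-organ effects. This stands as a caution: dependence on BP is plausible but not demonstrated.

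**The stakes are modest.** Sub-Aim 5F and Aim 7 are descriptive, and Aims 2-5 are exploratory and unpowered. Sub-Aim 5F concerns when the peak occurs, and a shift of this size need not move the peak day. This lowers the weight of the curve effect. It does not answer the misclassification of cases, nor the unequal capture between monitored women and controls.

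**Conclusion.** The concern holds in limited form. Appendix I has no BP field assigned to readmissions, emergency visits or triage visits. From 96 h to day 7, severe readings taken there may be missed, and hospital days may be absent from the 5F and Aim 7 curves. A woman with no other severe reading may be classed as a non-case for the Aim 2 hypothesis outcome and for the comparison of reported severe hypertension.

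The 0.15-3.0 mmHg range rests wholly on assumed occupancy and BP excess. A reader might be tempted to put a percentage on the lost cases. Any such figure would be a ratio of two invented inputs and should not be stated. Misclassification is the stronger reason to act. Some text between sections 11 and 13.1 was not available, so a rule there cannot be excluded. The change is worth making because it is cheap and the loss cannot be repaired later.

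**What to change.** - Add to Appendix I the first and maximum SBP and DBP, with date and time, for each readmission, emergency visit and triage visit through day 42. Do this for monitored women and controls alike. Amend the statement in section 6 that no fields will be added, if the 358 programme women are to be included.
- State which admission items 48-49 refer to, and which discharge items 68-69 refer to.
- Count a severe reading at any such encounter as a case for the severe-hypertension outcome. This needs one definition first: in section 6, the text on starting medication after discharge attaches SBP of at least 150 or DBP of at least 100 to severe hypertension, while the text on readmission uses 160 or 110. These passages must be reconciled.
- State how hospital days enter the 5F and Aim 7 curves, and show each curve with and without the hospital readings.

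The cost is minor extra abstraction, from charts already used for dates, drugs and laboratory values. The drawback is that hospital readings differ in method from averaged home readings, which is why both versions of the curves are needed.
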